9 SUBJECT POPULATIONS

9.1 Enrolled Set

The Enrolled Set includes all subjects who signed the informed consent form.

9.2 Allocated Set

The Allocated Set includes all subjects who are allocated to treatment. Presentation of the Allocated Set will be conducted according to the allocated treatment.

9.3 Safety Set

The Safety Analysis Set includes all subjects where the application of MAR-CUTIS or Dermabond Advanced has started. Subjects will be analyzed under the actual treatment received.

9.4 Full Analysis Set

The Full Analysis Set (FAS) includes all subjects randomized that were allocated to one of the 2 treatment groups and had at least 1 posttreatment efficacy assessment. Subjects from the FAS will be analyzed under the randomized treatment group.

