## 8.2 Follow-up Period

Subjects treated for lacerations may not be able to attend the Day 1 visit since they are usually not hospitalized. In this case, all attempts should be made to obtain information on potential dehiscence and AEs by phone. The reason for non-attendance should also be reported.

In case a subject is not able to attend the Day 10 visit, a telephone call can be done to capture the primary endpoint variables information. However, this is only allowed for exceptional cases and the reason for non-attendance and potential dehiscence and AEs should be recorded.

### 8.2.1 Day 1

The following procedures will be performed at Day 1:

- Record concomitant medication.
- Record AEs.
- Record of incidents and device performance, device-related complaints.
- Evaluation of dehiscence (incidence and grading).

### 8.2.2 Day 10 and Month 1

The product-related questionnaire will be completed by the investigator only once per site when the last subject randomized at the site completes the Month 1 visit.

The following procedures will be performed at both Day 10 and Month 1:

- Record concomitant medication
- Record AEs
- Record of incidents and device performance, device-related complaints

- 
- Evaluation of dehiscence (incidence and grading)
  - Evaluation of wound infection, if an infection occurred (incidence and criteria score)
  - Modified Hollander Cosmesis Scale (mHCS) completed by investigator
  - Subject-completed satisfaction questionnaire

Additional procedures performed at Month 1 include:

- Patient and Observer Scar Assessment Scale (POSAS), completed by subject and investigator
- Subject-related questionnaire completed by investigator
- Collect subject diary

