#### 10.1.1 Datasets or Populations Analyzed

- The Enrolled Set includes all subjects who signed the informed consent form (ICF).
- The Allocated Set includes all subjects who are allocated to treatment.
- The Safety Analysis Set includes all subjects where the application of MAR-CUTIS or Dermabond Advanced has started. Subjects will be analyzed under the actual treatment received.

- 
- The Full Analysis Set (FAS) includes all subjects randomized that were allocated to one of the 2 treatment groups and had at least 1 posttreatment assessment. Subjects from the FAS will be analyzed under the randomized treatment group.
  - The Per Protocol Set (PPS) defines a subset of subjects in the FAS without any major protocol deviations affecting the primary endpoint. Subjects from the PPS will be analyzed under the randomized treatment group.

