- 2) An analysis will be performed by repeating the logistic regression model described in the primary efficacy main analysis, albeit considering the length of the incision/laceration in the logistic regression model instead of the type of wound. This analysis will be performed using the FAS.
- 3) The primary efficacy analysis will be repeated, albeit by considering all subjects with missing data for the primary efficacy analysis as experiencing “Yes” dehiscence (ie, the wound did not remain closed). This analysis will be performed using the FAS.
- 4) An additional sensitivity analysis will be performed using a Cochran-Mantel-Haenszel (CMH; Cochran, 1954; Mantel and Haenszel, 1959) test. The dehiscence rates MAR-CUTIS:Dermabond will be analyzed with the CMH test, stratified by skin type (types I to III ; types IV to VI), age group (pediatric with age between 2 to 21 years; adult with age  $\geq 22$  years), type of wound (incision; laceration) and treatment (MAR-CUTIS; Dermabond Advanced). This analysis will be performed using the FAS.
- 5) A final sensitivity analysis will be performed by repeating the logistic regression model described in the primary efficacy main analysis, albeit introducing additionally the effect of the center where the subject was treated (given by the center ID) in the logistic regression model. This analysis will be performed using the FAS, and will only be considered if the logistic regression model converges.

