#### **10.1.3.2 Definition and Analysis of Secondary Efficacy Endpoints**

Secondary efficacy endpoints, as described in Section 6 are:

- Comparison of the dehiscence rate between MAR-CUTIS and Dermabond Advanced at the Month 1 or Early Discontinuation visit.

- 
- Score from POSAS recorded for the subject at Month 1 and Month 3/Early Discontinuation.
  - Comparison of wound infection incidence assessed on a binary scale ('1=yes' or '0=no') between both treatment groups. In addition, a total score will be calculated for each subject based on the wound infection assessed on the presence of erythema, edema, pain or elevated temperature (also assessed on a binary scale: "1=yes" or "0=no" for each characteristic).
  - Score from POSAS recorded for the investigator at Month 1 and Month 3/Early Discontinuation. Assessments will be presented by subject treated.
  - Score from mHCS recorded for the investigator at Day 10 and Month 1 or Early Discontinuation. Assessments will be presented by subject treated.
  - Score from a questionnaire related to subject experience and satisfaction with the device at Day 10 and at Month 1 or Early Discontinuation.
  - Scores from 2 investigator-completed questionnaires to evaluate overall satisfaction and ease of use with the device:
    - A product-related questionnaire to be completed for each center when the last randomized subject at the center completes the Month 1 visit or at Early Discontinuation. This assessment will be presented by center.
    - A subject-related questionnaire at Day 0 and Month 1 or Early Discontinuation. This assessment will be presented by subject treated.

Secondary efficacy endpoints will be summarized using descriptive statistics.

FAS will be used on all analyses.

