13.1.2 Sensitivity analysis

The following sensitivity analyses for primary efficacy will be performed:

- 1) The primary efficacy analysis as described above will be repeated using the PPS.
- 2) An analysis will be performed by repeating the logistic regression model described in the primary efficacy main analysis, albeit considering the length of the incision/laceration in the logistic regression model instead of the type of wound. This analysis will be performed using the FAS.
- 3) The primary efficacy analysis will be repeated, albeit by considering subjects with missing data for the primary efficacy analysis as experiencing “Yes” dehiscence (i.e., the wound did not remain closed). This analysis will be performed using the FAS. Descriptive statistics of dehiscence assessment following this second imputation rule will be added to the dehiscence descriptive statistics summary described in [Section 13.1.1](#).
- 4) An additional sensitivity analysis will be performed using a Cochran-Mantel-Haenszel (CMH; [Cochran, 1954](#); [Mantel and Haenszel, 1959](#)) test. The dehiscence rates MAR-CUTIS:Dermabond will be analyzed with the CMH test, stratified by skin type (types I to III ; types IV to VI), age group (pediatric with age between 2-21 years; adult with age ≥ 22

years), type of wound (incision; laceration) and treatment (MAR-CUTIS; Dermabond Advanced). This analysis will be performed using the FAS.

- 5) A final sensitivity analysis will be performed by repeating the logistic regression model described in the primary efficacy main analysis, albeit introducing additionally the effect of the center where the subject was treated (given by the center ID) in the logistic regression model. This analysis will be performed using the FAS, and will only be considered if the logistic regression model converges.

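### Protocol and SAP word the FAS differently, and under either wording the missing-as-dehiscence analysis does not reach treated subjects who have no qualifying post-treatment assessment

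*SAP*

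**What the plan says.** Protocol 10.1.1 puts in the FAS all randomised subjects who "had at least 1 posttreatment assessment". SAP 9.4 uses the same sentence with one more condition: they "had at least 1 posttreatment efficacy assessment". Both analyse subjects as randomised.

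The primary analysis uses the FAS (Protocol 10.1.3.1.2, SAP 13.1.1), and so do the main missing-data rules (Protocol 10.1.5, SAP 13.1.1). Those rules count as a failure anyone with a recorded earlier dehiscence, or whose reason for missing Day 10 is wound-related. Everyone else with missing data counts as a success. Sensitivity analysis 3 reverses this: the protocol repeats the primary analysis "albeit by considering all subjects with missing data for the primary efficacy analysis" as dehisced. Protocol 10.1.3.1.2, SAP 13.1.2 and the output list in SAP 16.2 all place that analysis on the FAS.

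Two other passages bear on who qualifies:

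- Protocol 8.2: "Subjects treated for lacerations may not be able to attend the Day 1 visit since they are usually not hospitalized". A phone call is to be attempted instead.
- Protocol 10.1.3.2 lists among the secondary efficacy endpoints "A subject-related questionnaire at Day 0 and Month 1 or Early Discontinuation". Protocol 8.1.2 has the Day 0 part completed after the device has been applied.

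**The concern.** The population for the primary analysis should have one definition, and here it has two. The SAP wording can also be read in two ways. If the investigator's Day 0 questionnaire is an efficacy assessment, as its place among the secondary efficacy endpoints suggests, nearly every treated subject qualifies. If an efficacy assessment means a check of the wound, a treated subject lost before the first check is out. Neither document settles this, and neither says whether information taken by phone counts.

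The consequence falls on sensitivity analysis 3. Its purpose is to show what happens if subjects with unknown outcome had dehisced. A subject who drops out of the FAS for lack of any assessment has the least information of all, yet is counted neither as a success nor as a dehiscence. With only a handful of events expected, a few such subjects could change what that analysis shows.

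**Working it through.** **Inputs.** Rates 3.05% and 0.85%, 126 versus 63 subjects, margin 8 points, one-sided 0.05 with a two-sided 90% interval, Farrington-Manning (FM) test (Protocol 10.2, SAP 5.2). The documents give no loss rate, so the numbers lost below are assumptions and are shown as a range.

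**The plan's own figure.** The stated power is 85%. Exact binomial enumeration of the FM test at these inputs gives 85.8%, so it reproduces. The asymptotic FM formula gives 79.2%.

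**Base case.** Expected events are 126 × 0.0305 = 3.84 and 63 × 0.0085 = 0.54, rounded to 4 and 1.

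**Formula.** With counts not adjusted for covariates,

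upper limit = d + 1.645 × SE, where SE = √[p̃M(1 − p̃M)/nM + p̃D(1 − p̃D)/nD]

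Here d is the observed difference, and p̃M and p̃D are the maximum-likelihood rates restricted to p̃M − p̃D = 0.08.

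Worked example, 7/126 versus 1/63: d = 5.56% − 1.59% = 3.97%. The restricted rates are 0.08875 and 0.00875, so SE = √(0.08875 × 0.91125/126 + 0.00875 × 0.99125/63) = 2.79%. The upper limit is 3.97 + 1.645 × 2.79 = 8.56%.

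| Lost before any qualifying assessment (MAR-CUTIS + Dermabond) | Left out of the FAS | Upper limit | Kept and counted as dehiscence | Upper limit |
|---|---|---|---|---|
| 1+0 | 4/125 v 1/63 | 6.09% | 5/126 v 1/63 | 6.88% |
| 2+0 | 4/124 v 1/63 | 6.13% | 6/126 v 1/63 | 7.71% |
| 3+0 | 4/123 v 1/63 | 6.18% | 7/126 v 1/63 | 8.56% |
| 2+1 | 4/124 v 1/62 | 6.11% | 6/126 v 2/63 | 6.58% |
| 4+2 | 4/122 v 1/61 | 6.19% | 8/126 v 3/63 | 7.15% |
| 6+3 | 4/120 v 1/60 | 6.26% | 10/126 v 4/63 | 7.72% |
| 8+4 | 4/118 v 1/59 | 6.34% | 12/126 v 5/63 | 8.28% |

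Each MAR-CUTIS subject counted as a dehiscence raises the difference by 1/126 = 0.79 points. Each Dermabond subject lowers it by 1/63 = 1.59 points. That is why 2:1 losses leave d at 1.59% and widen only the standard error.

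**Sensitivity to the base case.** The expected Dermabond count, 0.54, could as well be taken as 0. Then two MAR-CUTIS losses are enough: 6/126 versus 0/63 gives d = 4.76%, SE = 2.42% and an upper limit of 8.74%.

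**Effect on the main analysis.** A lost subject kept in the FAS with no sign of a wound problem counts as a success. For three MAR-CUTIS losses the upper limit is 6.04% (4/126 versus 1/63) if they are kept and 6.18% if they are left out.

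**Check on the interval.** Inverting the score test, instead of fixing the SE at the margin, gives 7.66% for 2+0, 8.66% for 3+0, 7.71% for 6+3 and 8.28% for 8+4. The same rows cross 8%.

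**The case against.** The case for leaving this alone has real force.

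- **The gap may be empty.** If the Day 0 questionnaire counts, nearly every treated subject is in the FAS. If it does not, every later contact has to fail, because Month 1 and Month 3 scar scores and the Early Discontinuation visit also yield efficacy data. Phone capture is allowed at Day 1 for lacerations and exceptionally at Day 10, and sites must try to reach all non-attenders. This stands as a limit on size. The main route left is a laceration subject who misses Day 1 and is then lost; about 40 lacerations are planned, 40/189 = 21%.
- **The decision does not rest on sensitivity analysis 3.** Noninferiority is declared on the main FAS analysis. This stands.
- **Losses in one arm only are a pessimistic pattern.** This stands too. With 2:1 losses, twelve never-assessed subjects are needed before 8% is crossed.
- **The plan looks beyond the FAS.** SAP Table 1 marks the primary endpoint for the safety set as well, and SAP 10.1 tabulates reasons for exclusion. This helps less: SAP 13.1.2 and 16.2 keep sensitivity analysis 3 on the FAS, and a tabulated subject is still not analysed.

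A reader might also infer three stronger points that the documents do not support:

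- **That the SAP changed the FAS without logging it.** SAP 7.1 has no FAS entry, but the SAP was written against the protocol dated 16 Jul 2018. The protocol in hand is version 4.0 of 25 Feb 2019, and the 2018 wording is not available.
- **That the SAP alone creates the gap.** The protocol FAS also drops a subject with no post-treatment assessment. The SAP wording adds only those with some other record but no efficacy record.
- **That the plan offers sensitivity analysis 3 as a worst case.** Neither document says so. Counting missing as dehiscence in both arms is in any case not the most adverse assignment for a noninferiority claim.

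**Conclusion.** The point holds, with limited size. The two FAS definitions differ, the SAP version is ambiguous, and under either one sensitivity analysis 3 omits treated subjects with no qualifying assessment, contrary to its stated coverage.

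In the base case of 4 versus 1 events, that analysis changes its answer only with three losses confined to MAR-CUTIS, or with about twelve split 2:1. With no Dermabond events, two MAR-CUTIS losses suffice. The main decision is practically unaffected. All of this rests on assumed losses and unadjusted counts; the planned estimate comes from a logistic model, so the exact limits would differ.

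This is a cheap improvement, not a threat to the trial's conclusion. It is worth settling before outcomes are reviewed, because the trial is open-label.

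**What to change.** 1. Use one FAS wording in both documents.
2. State whether a phone contact, and whether the investigator's Day 0 questionnaire, counts as an efficacy assessment.
3. Run sensitivity analysis 3 on all randomised subjects with study product applied, analysed as randomised, whether or not they had a post-treatment assessment. Product application is already the protocol's definition of treated (Protocol 7.3.1).
4. State explicitly how that analysis handles subjects withdrawn and replaced because the adhesive failed at application. They meet the definition of treated, and the current missing-data rules do not address them by name.

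Changing the analysis set for sensitivity analysis 3 is better than simply widening the FAS to everyone treated. A wider FAS would bring never-assessed subjects into the main analysis as successes and make it slightly more lenient.

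The cost is a few sentences in each document, with no new data and no change to the margin or sample size. The downside is that sensitivity analysis 3 may come out slightly less favourable.

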9.5 Per Protocol Set

The Per Protocol Set (PPS) defines a subset of subjects in the FAS without any major protocol deviations affecting the primary endpoint. Subjects from the PPS will be analyzed under the randomized treatment group.

10 DISPOSITION

10.1 Subject disposition

All presentations for subject disposition will be by treatment group and overall.

For describing the subject disposition, the following populations will be summarized overall and for the subgroups described in Section 8.2.1.

- Subjects enrolled (only overall).
- Subjects enrolled but not allocated and reason for non-allocation.
- Subjects allocated.
- Subjects allocated but not treated and the reasons for not being treated.
- SAF.
- FAS.
- Trial completers.
- Subjects allocated and discontinued from the trial.

For subjects enrolled but not allocated and for the reasons for not being allocated, the percentage denominator will be the number of enrolled subjects. For the reasons for not being treated for subjects allocated but not treated, the percentage denominator is the number of allocated but not treated. For all other calculations, the percentage denominator will be the number of allocated subjects.

In addition, an overview table will be prepared presenting the number of subjects enrolled, allocated, in the SAF, and in the FAS per country. Percentage calculation will be done in 2 ways:

- Denominator will be the number of all allocated subjects.
- Denominator will be the number of allocated subjects in the respective country.

Reasons for exclusion from the analysis populations will be summarized. The percentage denominator will be the number of subjects allocated.

10.2 Subject discontinuations

Discontinuations from the trial will be presented for the SAF overall.

Reasons for discontinuations from the trial will be presented for

- Subjects discontinued from the trial.
- Subjects discontinued from the trial for the subgroups described in Section 8.2.1.

Percentage denominator will be the number of subjects discontinuing in the respective group.

The details for “other reasons” will be listed and included in the subject discontinuation frequency table, if applicable.

10.3 Protocol deviations

Major protocol deviations will be presented overall and by center for the SAF. They will be grouped into categories as collected and summarized descriptively.

Major protocol deviations will be presented in a subject data listing.

11 DEMOGRAPHICS AND OTHER BASELINE CHARACTERISTICS

No statistical tests for comparison of demographic and baseline data between treatment groups will be performed.

Subject demographics and baseline characteristics will be summarized descriptively by treatment group and overall. Subject demographics and other baseline characteristics will be descriptively summarized for the SAF and the FAS. An additional summary will be provided by country for the SAF and FAS. Subject demographics will also be presented for the enrolled set; presentation will be without treatment group but only for overall.

11.1 Subject demographics

Subject demographics are age [years], weight [kg], height [m], body mass index (BMI) [kg/m²], sex, race, ethnicity and age group. All data will be reported as recorded in the e-CRF.

Age groups will be ≥ 2 years and < 12 years, ≥ 12 years and < 18 years, ≥ 18 years and < 65 years, ≥ 65 years and < 85 years, and ≥ 85 years. Additionally, as a separate block also the age groups pediatric ≥ 2 years and < 22 years and adult ≥ 22 years will be presented.

11.2 Other baseline characteristics

The remaining other relevant baseline characteristics will be descriptively summarized:

Continuous baseline characteristics are: length of target wound.

Categorical baseline characteristics are: Skin type, type of target wound, current smoking status, alcohol abuse and if the target wound required deep suturing.

11.3 Subject medical and surgical history

Diseases and surgical interventions are presented as “prior” or “concomitant” as documented by the investigator (i.e., “concomitant” will be documented as “Ongoing” in the e-CRF).

Medical and surgical history will be summarized and sorted alphabetically, separately for prior and concomitant, by SOC and Preferred Term (PT). The number of subjects will be displayed for each SOC and PT.

The target wound description (for incisions and lacerations) will be recorded in the e-CRF, summarized and listed.

11.4 Prior and concomitant medication

Prior and concomitant medication is collected in the e-CRF as per enrollment. For the analysis, the following algorithm will be used to define prior and concomitant medication:

- Prior is all medication stopped before the start of the application of the IMD, regardless of its start date.
- Concomitant is any medication not stopped before the start of the application of the IMD, regardless of its start date or medication started after the start of the application of the IMD.

Medication will be summarized and sorted alphabetically separately for prior and concomitant medication by Anatomical Therapeutic Chemical categories (Level 2: pharmacological or therapeutic subgroup and Level 3: chemical or therapeutic or pharmacological subgroup).

For each medication, the number of subjects will be displayed. In addition, for concomitant medication the number of subjects with medication taken while the glue remains attached (i.e., the glue is not detached nor intentionally removed) will be displayed in the same summary table.

Medication started after the the glue is detached or intentionally removed will be flagged in the subject data listing.

12 EXPOSURE AND COMPLIANCE

12.1 Exposure

Exposure to the IMD will be presented in days and summarized for each subject using the following formula:

Treatment exposure = date and time of glue detachment or removal – date and time of application of the IMD

For the formula above, the time of glue detachment or removal will be used only if it is recorded in the e-CRF (recorded for on-site assessments, but not recorded for the subject diary).

If no glue detachment or removal was applicable, the exposure will be calculated instead with the formula:

Treatment exposure = date of study completion or early withdrawal – date and time of application of the IMD

Treatment exposure will be reported in days rounding to one decimal place.

Treatment exposure will also be assessed using the following (as recorded in the e-CRF for IMD application and performance):

- Number of syringe(s) used for glue application
- Total volume used (mL)

12.2 Compliance

The IMD will only be applied on Day 0 by the medical practitioner. The type of IMD and , whether the IMD was applied to the target wound will be recorded in the e-CRF and summarized descriptively.

Additionally, a summary of the wound exposure to water will be presented including whether the wound was exposed and the number of days. This summary will be presented separately for subjects with or without early glue detachment or removal.

